5.1 Primary outcome

The primary outcome will be the change in patient functional assessment compared to the baseline, measured through the Constant Score.

5.2 Secondary outcomes

The secondary outcomes will be:

- The change in patient reported function in comparison to the baseline, measured by the QuickDASH score
- The change in shoulder range of motion in comparison to the baseline, measured by the shoulder flexion degree in a sitting position (in degrees)

6. Sample size estimate

Sample size estimation was performed taking into consideration the primary outcome measure – The Constant Score - and a non-inferiority scenario.

In the absence of similar studies, the calculations were made taking into account the study by Arndt *et al.* (2012)⁴⁰. This was a large study (n=100 patients) which compared two different rehabilitation protocols after ARCR and which used the same primary outcome as our study. In this study, the standard deviation of the Constant

Score at baseline was 12.0. A Minimal Clinically Important Difference (MCID) of 10.4 was considered, based on the study by Constant *et al.* (2008).⁵⁵

Considering a power of 90%, a two-sided 0.05 significance level and a 10% dropout rate, 68 patients would be necessary to detect a 10.4 points difference between the two groups.

7. Location of Recruitment

Patients will be recruited at Hospital da Prelada - [name] da Cruz.

8. Inclusion criteria

- a) Patients over 18 and under 70 years old
- b) Shoulder pain and functional limitation with clinical examination compatible with reparable rotator cuff tear
- c) Imaging (MRI or ultrasound) evidence of rotator cuff tear (supra and/or infraspinatus tendon tear inferior to 5cm)
- d) Indication for a rotator cuff repair according to the patient's orthopedic surgeon
- e) Ability to understand simple and complex motor commands
- f) Availability of a carer to assist the patient after surgery

9. Exclusion criteria

Preoperative

- a) Patients with indication for revision cuff repair
- b) Complex cuff tears (involving subscapularis tendon or more than one tendon besides supra and infraspinatus, or massive dimension tears)

- c) Glenohumeral arthritis
- d) Irreparable tendon defect
- e) Patients with concomitant neurological disorders (ex. Stroke, Parkinson's disease, multiple sclerosis)
- f) Aphasia, dementia or psychiatric comorbidity interfering with the communication or compliance to the rehabilitation process
- g) Respiratory, cardiac, metabolic conditions or others incompatible with at least 30 minutes of light to moderate physical activity

Postoperative

- h) Irreparable tendon lesion
- i) Major medical complications occurring after surgery that prevent the discharge of the patient within 5 days after surgery
- j) Other medical and/or surgical complications that prevent the patient from complying with a rehabilitation program
- k) Blind and/or illiterate patients

10. Methods for identifying and recruiting patients

All patients admitted for rotator cuff repair during the study period will be screened for inclusion and exclusion criteria.

When a potential candidate is identified, the local investigator will approach the candidate and explain the study in detail. The prospective candidate will be given the patient information document and sufficient time to consider whether he wishes to participate in the study.

Subsequently, the prospective candidate will be given opportunity to clarify any

doubts, after which the informed consent form will be signed and dated in duplicate by the patient and the investigator. Only then will the randomization and baseline assessments be performed.

11. Patient allocation to study groups

For logistic reasons, the study will be restricted to patients living in a 20km radius around the investigation center. Patient allocation to the two groups will be performed in a random way, in a 1:1 ratio in blocks of six. This will be done using an online randomizer (<https://www.randomizer.org>).

The allocation of patients to each group will be performed centrally by one investigator - [name] - and communicated to the responsible for data acquisition only after patient enrollment. This investigator will not be involved in data collection or in outcomes assessment.

12. Blinding

The nature of the study does not allow blinding of the patients regarding study groups. However, participants will be blinded to the primary and secondary outcomes being measured. All patient assessments will be performed by an investigator blinded for randomization groups. Statistical analysis will be performed blinded for randomization group.

13. Patient assessment

Patients will be assessed pre-operatively, and then at 6, 12, 16 and 20 weeks after the surgery. In patients where a decision is made to extend the program to 24 weeks,

another assessment will be made at this point. An assessment will also be made at 12 months after surgery.

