13.1 Baseline assessment

Participant characterization will consist of:

- a) Demographics (gender, date of birth);
- b) Educational level (years);
- c) Affected side
- d) Injured structures
- e) Size of tear
- f) Date of surgery
- g) Comorbidities
 - a. Factors affecting tissue healing: Smoking, Diabetes, Steroid intake
 - b. Other disorders: cardiac, respiratory, hypertension
 - c. Time between diagnosis and surgery
- h) Body Mass Index
- i) Constant score
- j) QuickDASH
- k) Shoulder range of motion

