Patients in the active comparator group will receive face-to-face rehabilitation sessions provided by a physical therapist. Therefore, patient safety will be ensured at all times during the sessions. Patients will be able to report adverse events to their physical therapist. Moreover, the patient's orthopedic surgeon will be notified in case of detrimental clinical progression, so that the patient can be re-evaluated.

For patients in the experimental group, safety of the remote sessions will be evaluated through pain and fatigue scores (graduated from 0 to 10) collected at the end of each session. These will be presented to the patient using the mobile App and will be available for remote monitoring by their physical therapist. In case of excessive pain or fatigue, patients will be contacted by their physical therapist to ascertain the cause and change prescription if needed. Patients will also be asked to report any other adverse events to their physical therapist by telephone. Moreover, the patient's orthopedic surgeon will be notified in case of detrimental clinical progression, so that the patient can be re-evaluated.

The adverse events will be registered in the patient's file (beginning date, resolution date (if applicable), resolution state, severity).

16. Statistical analysis

To assess differences in clinical and demographic variables of the patients allocated to the two study groups, independent samples t test or Mann-Whitney U test will be used for quantitative variables. For qualitative variables, Chi-squared test or Fisher's exact test will be used.

Outcome analysis will be performed using a per-protocol analysis. The impact of the interventions in the primary and secondary outcomes will be evaluated considering

the change between baseline and week 20. Differences between the two study groups will be performed using independent samples t test or Mann-Whitney U test.

Since outcomes will be measured in several different times during the rehabilitation program, a repeated measures analysis will also be performed, using a 3x2 ANOVA with group as an independent factor and time as a within-subjects factor.

17. Potential Risks and Benefits to Participants

There are no invasive procedures involved in this research protocol and, given the nature of the intervention, no relevant risks are foreseen.

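### The sample size uses the SD of the baseline Constant Score, but the planned test is on unadjusted change to week 20, so the 90% power is unsupported

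*Combined protocol and SAP*

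**What the plan says.** Section 6 bases the calculation on the Constant Score in "a non-inferiority scenario". Its SD comes from a cited 100-patient trial of two rehabilitation protocols, where the Constant "Score at baseline was 12.0". With a 10.4-point difference, 90% power, two-sided 0.05 and 10% dropout, it concludes that "68 patients would be necessary to detect a 10.4 points difference between the two groups".

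The analysed variable is different. Section 5.1 states: "The primary outcome will be the change in patient functional assessment compared to the baseline, measured through the Constant Score". Section 16 evaluates "the change between baseline and week 20" and continues: "Differences between the two study groups will be performed using independent samples t test or Mann-Whitney U test". No covariate is named. Section 16 adds that "a repeated measures analysis will also be performed, using a 3x2 ANOVA with group as an independent factor and time as a within-subjects factor".

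The baseline value is available for every patient: Section 13.1 lists "i) Constant score" among the baseline assessments. No SD of change, week-20 SD or correlation between baseline and week 20 appears anywhere in the protocol.

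**The concern.** The SD in Section 6 describes patients before surgery. The test in Section 16 is on how much they change after surgery and 20 weeks of follow-up. The two SDs agree only under particular values of the week-20 SD and the correlation, and the plan neither states nor defends those values. If the change SD is larger than 12, the trial has less power than claimed. In a trial meant to show that the digital programme is no worse, the confidence interval would then be wider than planned, and a truly similar programme could end with an inconclusive result.

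The plan also uses the baseline score inefficiently. Subtracting it fixes its coefficient at 1, whereas a regression model estimates the coefficient and usually leaves less residual variance.

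**Working it through.** **Inputs from the protocol.** SD 12.0, difference 10.4, power 90%, two-sided 0.05, 10% dropout and total 68 (Section 6); 1:1 allocation (Section 11); change to week 20, unadjusted (Section 16).

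**Inputs not in the protocol.** The week-20 SD, *s*, and the baseline to week-20 correlation, *r*. Both are assumptions and are varied below.

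**Step 1: reproduce 68.**
- Normal approximation, per arm: n = 2 × (1.960 + 1.282)² × (12/10.4)² = 27.98, so 28. Dividing by 0.9 gives 32 per arm, 64 in total.
- Exact t test: 29 per arm, 33 after dropout, 66 in total.
- Mann-Whitney with efficiency 3/π under normality: 31 per arm, 62 in total. Then 62 × 1.1 = 68.2 and 62/0.9 = 68.9; rounding up per arm gives 70.

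So 68 is reproduced to within about two patients when 12.0 is taken directly as the SD of the analysed variable.

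**Step 2: SD of the variable actually tested.**
- Change score: SD = √(12² + *s*² − 24*rs*).
- Baseline-adjusted: residual SD = *s*√(1 − *r*²).
- Difference in variance, change minus adjusted: (12 − *rs*)², never negative.

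With *s* = 12, the change SD is √(288 − 288*r*), which equals 12.0 only at *r* = 0.5.

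**Step 3: power with 61 evaluable patients** (68 × 0.9 = 61.2), noncentral t, 59 degrees of freedom unadjusted and 58 adjusted. Power at SD 12 is 91.4%. The largest SD that still gives 90% is 12.32. The break-even correlation for the change score is therefore *r* = (144 + *s*² − 12.32²)/(24*s*).

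| Assumed *s* | *r* needed for 90%, change | Power at *r* = 0.3, change / adjusted | Power at *r* = 0.5, change / adjusted |
|---|---|---|---|
| 10 | 0.38 | 86% / 99% | 95% / >99% |
| 12 | 0.47 | 80% / 94% | 91% / 97% |
| 14 | 0.56 | 73% / 85% | 86% / 91% |
| 16 | 0.65 | 66% / 74% | 79% / 82% |
| 20 | 0.82 | 51% / 55% | 63% / 64% |

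Worked cell, *s* = 12 and *r* = 0.3: change SD = √(288 − 86.4) = 14.20, power 80%; adjusted SD = 12 × √0.91 = 11.45, power 94%. At *s* = 12 and *r* = 0.4, unadjusted power is 86%.

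**Step 4: when adjustment is enough.** The adjusted SD never exceeds *s*, so any *s* up to about 12.3 gives at least 90% for every *r* ≥ 0. Above that, adjustment needs *r* of about 0.475 at *s* = 14, 0.64 at *s* = 16 and 0.79 at *s* = 20.

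**Step 5: patients needed if *s* = 14 and *r* = 0.3.** Adjusted SD 13.36: 72 evaluable, 72/0.9 = 80 enrolled. Change SD 15.47: 96 evaluable, 96/0.9 = 107 enrolled.

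**Step 6: Mann-Whitney.** With normal data and efficiency 0.955, the break-even *r* at *s* = 12 rises from 0.47 to about 0.50.

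**The case against.** Unsupported does not mean underpowered. If the two SDs are equal and *r* is 0.5, the change SD is exactly 12.0 and 68 patients give 91%; at *s* = 10, a correlation of 0.38 is enough. The lowest powers in the table come from *s* = 16 and 20, which nothing in the protocol supports. This stands, and the case to read first is *s* = 12.

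The change-score test is valid, so preferring the adjusted model is a gain in efficiency and not the correction of an error. A justified change SD alone would close the gap in Section 6. This also stands, but the adjusted model uses data already collected and makes the stated power less dependent on the unknown correlation.

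The gain is not strictly free. The adjusted formula leaves out chance baseline imbalance, which multiplies the expected variance by about 1 + 1/57 = 1.0175 with 61 patients. That moves the 12.3 threshold to about 12.2 and lowers the tabulated adjusted powers by less than one percentage point. Adjustment can lose trivially when *r* is near 12/*s*. At *s* = 20 and *r* = 0.5, for instance, the variances are 304 for change and 300 × 1.0175 = 305 adjusted. The comparison for *s* from 10 to 16 is essentially unchanged.

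The repeated-measures ANOVA is a weaker point. It is additional, and Section 16 does not say which three times it uses; if baseline is one of them, it already enters as an outcome level.

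**Conclusion.** The concern holds. The figure of 68 is not miscalculated, but its 90% power applies to the planned test only if an unstated condition is met: *r* of about 0.47 or more at a week-20 SD of 12, and higher if that SD is larger. At *s* = 12, unadjusted power runs from 80% to 91% as *r* goes from 0.3 to 0.5; baseline adjustment gives 94% to 97%. Adjustment usually helps, but it does not guarantee 90% once the week-20 SD exceeds about 12.3, and it gains almost nothing at *s* = 20 and *r* = 0.5.

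These results assume 61 evaluable patients, a baseline SD of 12, a difference of 10.4 and normal data. Section 16 plans a per-protocol analysis, so exclusions beyond the 10% dropout would lower all the powers. No bias is claimed. This is a change that should be made, at little cost.

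**What to change.** **Section 16.** Make the primary analysis a linear model of the week-20 Constant Score (or its change) on group and baseline Constant Score, reporting the adjusted difference with its 95% confidence interval. Name one sensitivity analysis for clearly non-normal residuals, such as a bootstrap interval or a rank-based model with the same covariate, in place of the open choice between two tests. The same model form serves QuickDASH and shoulder flexion, each with its own baseline value. The interval has to be read against a stated non-inferiority margin; Section 6 gives 10.4 only as a clinically important difference and as the difference to detect, so the margin needs to be settled separately.

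**Section 6.** Justify an SD of change, or a week-20 SD and correlation. Failing that, give power as a range over both quantities, as in the table above.

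**Cost.** Wording in two sections and one covariate that is already collected. Adjustment itself needs no extra patients. If the justified week-20 SD is above about 12.3, the sample size may have to be revisited: at *s* = 14 and *r* = 0.3, 80 enrolled with adjustment against 107 without.

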13.1.3 Shoulder range of motion

The shoulder range of motion will be measured in the sitting position.

The system used in the study is a validated medical device for joint angle measurement. Therefore, shoulder range of motion will be measured automatically

SH-RCT-ARCR-01 Study Protocol

by the system.

In this study, active range of motion will be measured in the following movements:

- a) Elevation of the shoulder in the scapular plane, sitting: with the patient sitting, with the arm fully extended, have the patient actively raise the arm in the scapular plane as much as possible, with extended elbow.
- b) Sitting shoulder flexion: with the patient sitting, with the arm fully extended, have the patient actively raise the arm as much as possible, with extended elbow.
- c) Sitting Shoulder Abduction: with the patient sitting, with the arm as close as possible to the body, have the patient actively open the arm as much as possible, with extended elbow.
- d) Sitting Shoulder External Rotation: with the patient sitting with 90° bent elbow and hand pointing forward, have the patient actively rotate the arm outwards, as much as possible.

In order to achieve this, the investigator will need to:

- 1) Create a new patient in the Phoenix Portal
- 2) Prescribe these four different exercises, described above
- 3) Setup SWORD Phoenix
- 4) Ask the patient to perform five repetitions of each movement to the best of his ability, while SWORD Phoenix records movement parameters
- 5) After the session, login to the Portal, go to the session's results and click on detailed results for each exercise. Record the value of best repetition for each exercise in the patient file.

13.2 Assessments at 6, 12, 16, 20 (and/or 24) weeks after surgery and assessment

12 months after surgery

These assessments will include:

- a) Constant score
- b) QuickDASH
- c) Shoulder range of motion (as described for the baseline assessment)

14. Intervention

Both study groups will receive early-onset home-based rehabilitation for 20 weeks, starting two weeks after surgery.²⁸ This program can be extended for another 4 weeks if necessary.

The experimental group will perform daily home-based rehabilitation sessions using SWORD Phoenix, under remote monitoring by a physiotherapist, as well as home one-to-one physiotherapy sessions, with decreasing periodicity depending on program stage.

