The conventional rehabilitation group will receive home-based rehabilitation provided by a physiotherapist, 3 times a week, for 1 hour. Patients will also be instructed to perform additional unsupervised sessions in at least two other days of the week. Compliance to these additional sessions is not mandatory, but patients will be asked to fill in a diary regarding these extra-sessions.

The intervention arm, additionally to the one-to-one sessions, will perform daily home-based rehabilitation sessions using the system alone, under remote monitoring

SH-RCT-ARCR-01 Study Protocol

by a physiotherapist. Patients will be instructed to perform exercise sessions at least 5 times per week, but compliance to that frequency is not mandatory per protocol. The number of sessions, daily adherence and total training time will be registered automatically by the system and will be made available through the Web Portal, from where it can be transcribed to each patient file. When required, additional visits or telephone calls for technical assistance can be performed by the physical therapist. These will be registered as such in the patient file.

In the absence of a gold standard, the rehabilitation protocols were designed taking into account: a) a recent systematic review on the subject;⁴ b) a review of the concepts and evidence-based guidelines on this subject by van der Meijden *et al.* (2012)¹⁵; c) an overview of systematic reviews comparing early and conservative rehabilitation²⁸ and d) the protocol of the Massachusetts General Hospital for rehabilitation after rotator cuff repair.

The rehabilitation program will be based on the principles outlined in the following tables 1-4. In any case, these protocols can be tailored to the patient's specific needs, according to the assessment of the orthopedic surgeon and the physical therapist.

Table 1. Immediate Post-op Phase

Rotator cuff repair program: Immediate Post-op Phase (weeks 0 to 2) - Immobilization period	
Goals	Precautions
Control pain and swelling	
Protect the rotator cuff repair	Do not lift the operated arm
Protect wound healing	
Prevent shoulder stiffness	
Intervention	
Conventional PT group	Experimental Group
Use of a sling during the day and during the night until week 4	
Ice pack application to the operated shoulder for 15 minutes if necessary to reduce pain and swelling several times per day	
Promote the active movement of fingers, hand and elbow to increase circulation	

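### Randomisation appears to sit before surgery while three eligibility criteria can only be judged after it, one of them by open-ended, unprotected judgement; randomising in the common weeks 0-2 would avoid this

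*Combined protocol and SAP*

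**What the plan says.** **Order of events.** Section 10 describes consent and then states "Only then will the randomization and baseline assessments be performed". Section 13 fixes when the baseline is taken: "Patients will be assessed pre-operatively, and then at 6, 12, 16 and 20 weeks after the surgery". No section dates randomisation relative to surgery.

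**Criteria listed as postoperative.** Section 9 has four under that subheading:
- (h) a lesion found to be beyond repair, worded as "Irreparable tendon lesion"
- (i) a serious complication that delays discharge past day 5
- (j) a residual clause on ability to take part: "Other medical and/or surgical complications that prevent the patient from complying with a rehabilitation program"
- (k) blindness or illiteracy

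**When the arms diverge.** Section 14 says "Both study groups will receive early-onset home-based rehabilitation for 20 weeks, starting two weeks after surgery". Table 1, headed "Rotator cuff repair program: Immediate Post-op Phase (weeks 0 to 2) - Immobilization period", gives one set of measures for both groups. The schedule of face-to-face sessions shows 0 against 0 in weeks 1 and 2, then 2 (conventional) against 1 (experimental) in week 3.

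**Blinding and analysis.** Section 12 says patients cannot be blinded, while outcome assessors and the statistical analysis are. Section 11 releases the allocation after enrolment to the person responsible for data acquisition. Section 16 specifies a per-protocol analysis. It has no analysis of all randomised patients and no rule for a patient found ineligible after allocation.

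**The concern.** A site that follows Sections 10, 13 and 9 in order consents and randomises the patient, sees the operation done, and then decides whether the patient was eligible. Exclusions made after allocation keep the groups comparable only if they cannot depend on the arm.

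Criterion (j) offers no such assurance. It asks whether someone can cope with rehabilitation, and the two programmes differ: 52 scheduled face-to-face sessions against 19 plus daily device sessions. The decision could therefore be coloured by the assignment. It also has no closing date, so it could be applied after week 3, when the treatments have already diverged.

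The direction matters. The hypothesis in Section 2 is that the device programme is at least similar, and Section 6 plans for non-inferiority. Losing patients with a poor outlook from the device arm would favour that conclusion. The per-protocol analysis would not bring them back, and outcomes that were never collected cannot be recovered later.

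**Working it through.** **1. The plan's sample size.** Inputs from Section 6: difference 10.4, SD 12.0, two-sided 0.05, power 90%, dropout 10%, total 68.
- Normal approximation: n per arm = 2 × [12 × (1.960 + 1.282) / 10.4]² = 27.98, so 28. With dropout, 28/0.9 gives 32 per arm, 64 in total.
- Exact t: 29 per arm; 29/0.9 gives 33 per arm, 66 in total.
- Mann-Whitney, efficiency 0.955 (assumed; Section 16 names the test as an alternative): 28/0.955 gives 30; 30/0.9 gives 34 per arm, 68 in total.

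The figure of 68 is reproducible and is not in dispute.

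**2. Which criteria can bias the comparison?**

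| Criterion | When it can be known | Consequence if applied after randomisation |
|---|---|---|
| (h) | At surgery | Before the arms differ; mainly costs numbers |
| (i) | Within 5 days of surgery | Before the arms differ; mainly costs numbers |
| (j) | No limit stated | Judgement, possibly after week 3; can depend on the arm |
| (k) | Before surgery | Not a surgical event; misplaced in the list |

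**3. Cost in numbers.** 68 × 0.9 = 61.2 evaluable, so the dropout allowance is 6.8 patients. The documents give no rate of post-operative exclusion, so the rates below are assumptions, applied on top of the 10% dropout. Power is by normal approximation with the planning SD.

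| Excluded | Patients of 68 | Evaluable | Power |
|---|---|---|---|
| 0% | 0 | 61.2 | 0.92 |
| 5% | 3.4 | 58.1 | 0.91 |
| 10% | 6.8 | 55.1 | 0.90 |
| 20% | 13.6 | 49.0 | 0.86 |

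**4. Upper bound on bias from selective removal.** Suppose the k lowest scorers of 34 are removed from one arm and nobody from the other. With normal scores and p = k/34, the arm's mean rises by SD × φ(z_p)/(1 − p).

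| k | p | φ(z_p) | Shift, SD 12 | Share of 10.4 | Shift, SD 20 (assumed) |
|---|---|---|---|---|---|
| 1 | 0.029 | 0.067 | 0.83 | 8% | 1.38 |
| 2 | 0.059 | 0.117 | 1.50 | 14% | 2.49 |
| 3 | 0.088 | 0.160 | 2.11 | 20% | 3.51 |

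Simulated samples of 34 give slightly smaller shifts at SD 12: 0.77, 1.42 and 2.02.

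**5. What such a shift does to a non-inferiority conclusion.** Take 10.4 as the margin (an assumption; Section 6 calls it the minimal clinically important difference) and 61.2/2 = 30.6 evaluable per arm. Then SE = 12 × √(2/30.6) = 3.07. The one-sided error at the margin is Φ(shift/3.07 − 1.96): 0.025 with no shift, and about 0.046, 0.071 and 0.102 for shifts of 0.83, 1.50 and 2.11.

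**The case against.** **The timing is inferred.** This is correct. Section 13 makes the assessment pre-operative but does not say so of randomisation. The baseline list in Section 13.1 includes date of surgery, injured structures and tear size, so the record may not close before the operation. Section 11 does not define enrolment, which could be meant to follow the post-operative checks. But pre-operative randomisation is the natural reading of Sections 10 and 13, and nothing places it later. If the sponsor intends randomisation after surgery, the protocol still has to say so.

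**A reader might infer that exclusions are made with the arm known.** The documents do not support that. They do not say who applies criterion (j) or what that person knows. What they show is the absence of a safeguard: blinding covers outcome assessment and analysis, not eligibility decisions.

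**A reader might also infer that all four criteria threaten the comparison.** They do not. Criterion (k) can be settled before surgery, and (h) and (i) arise before care differs.

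**Criterion (j) is worded neutrally as to arm.** It refers to a rehabilitation programme in general. Section 14 does not make the device-session frequency mandatory, and the experimental arm also receives therapist visits. So the text does not invite exclusion because device sessions are hard. It does not prevent it either, and the criterion still has no definition, limit or decision maker.

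**The bias figures are a worst case.** Agreed. They take exactly the lowest scorers from one arm only. They also use a baseline SD for an outcome that is a change score, and SD 20 appears nowhere in the documents.

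**The loss of power is minor.** Agreed. At 10% exclusion the planned 90% is essentially kept.

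**Conclusion.** The point stands in a limited form. On the natural reading of Sections 10 and 13, patients are randomised before surgery and can then be excluded under (h) to (j). The threat to validity lies mainly in (j), because it is discretionary and open-ended in a trial where patients know their arm and outcomes are analysed per protocol only.

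The mean shifts of 0.8, 1.5 and 2.1 points at SD 12 are upper bounds for one, two or three exclusions confined to one arm. They are not estimates of what will happen. They are modest against 10.4. On the assumption that 10.4 serves as the margin, they could still raise a nominal 2.5% one-sided error to at most about 10%. The effect on power is small, about 0.92 to 0.90 at an assumed 10% exclusion.

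The case for acting rests less on the size of the bias than on how easily it is avoided: nothing in weeks 0-2 requires the arm to be assigned.

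**What to change.** **Sections 9 to 11**
- Keep consent and the baseline assessment before surgery.
- After surgery, check and record criteria (h) to (j). Then randomise within the common weeks 0-2 and before the first week-3 session. State this timing explicitly.
- Move (k) to the preoperative list.
- State that no patient is excluded on eligibility after randomisation.

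**Section 16**
- Moving randomisation does not deal with complications that arise later. State that these patients stay in follow-up and in an analysis of all randomised patients, and report any removals from the per-protocol analysis by arm.

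**If randomisation must stay before surgery**, the weaker alternative is to have (j) decided within a fixed window by someone unaware of the arm, keep all randomised patients in the analysis, and report exclusions by arm.

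**Cost.** The changes are to protocol wording, with no extra visits or staff. The allocation must be released within a two-week window so that week-3 sessions can be booked. Some consented, baseline-assessed patients will not be randomised, so slightly more must be consented to reach 68: 68/0.95 gives 72 if 5% are excluded, and 68/0.90 gives 76 if 10% are (both rates assumed).
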